Debriefing: Participants will return to the lab for a final session at which they will complete a final DEQ rating of how much they liked each study drug and how much they would want to take each study session drug again. Participants will also be asked to report which type or types of drugs they think they received at each session. Finally, participants will be fully debriefed with regard to the study hypotheses, methods and the types of drugs that they received, and will be given a chance to ask any final questions.

Data Analysis

IAPS: We hypothesize that participants will react less to negative pictures while taking CBD, while reactions to positive and neutral slides will be unchanged. We will conduct a Mixed Linear Model analysis in R using lme4 on each dependent variable (subjective ratings, corrugator and startle responses) using Drug (0, 300, 600 and 900mg) and picture type (positive, neutral, negative) as independent variables, and including random variables for Subject and Drug.

DEIT: We hypothesize that participants will show decreased sensitivity to negative facial expressions (anger, sadness and fear) on CBD, as measured by a greater intensity of expression required to identify negative facial expressions, but unchanged intensity for happy facial expressions. We also hypothesize that CBD will reduce negative psychophysiological responses to negative facial expressions, but not happiness. We will conduct a Mixed Linear Model analysis in R using lme4 on each dependent variable (expression intensity and corrugator responses) using Drug (0, 300, 600 and 900mg) and expression type (happy, angry, fearful, sad) as independent variables, and including random variables for Subject, Drug and Actor.

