ABT: We hypothesize that participants will show reduced attentional bias to negative facial expressions (anger, sadness and fear) on CBD, as measured by increased reaction times for probe response for negative faces, without any change in responses to happy faces. We will conduct a Generalized Mixed Linear Model analysis in R using lme4 on the binomial variable of initial gaze direction with Drug (0, 300, 600 and 900mg) and expression type (happy, angry, fearful, sad) as independent variables, and including random variables for Subject and Drug. We will conduct a Mixed Linear Model analysis in R using lme4 on total dwell time on each face, using Drug (0, 300, 600 and 900mg) and expression type (happy, angry, fearful, sad) as independent variables, and including random variables for Subject and Drug.

IST: We hypothesize that participants will show increased talkativeness on the IST, as measured by total word count and further, that this increased talkativeness will be mediated by reduced negative responses to negative emotional and social cues (as measured in the IAPS, DEIT and ABT). We will first derive per-participant estimates of the effect of drug on responses to negative stimuli from the Mixed Linear Model analyses described above. We will then conduct a Mixed Linear Model analysis in R using lme4 on total word count with Drug (0, 300, 600 and 900mg) as an independent variable, and including random variables for Subject and Drug (per Wardle et al. 2012b). Following criteria for within-subject mediation (Judd et al. 2001), we will first establish whether drug has the hypothesized effect on talkativeness. We will then include the per-participant estimates of the effect of drug on responses to negative stimuli as covariates, and examine 1. Whether changes in responses to negative stimuli account for a significant proportion of changes in talkativeness, and 2. Whether the effect of drug on talkativeness is still significant after inclusion of the changes in responses to negative stimuli. If the effect of drug on effort is wholly mediated by changes in responses to negative stimuli, we would expect the effect of drug on talkativeness to no longer be

significant after including drug-induced changes in responses to negative stimuli as a covariate (see Wardle and de Wit 2012 for an example of this type of analysis).

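### Losing significance for Drug after the mediator is added cannot tell whole from partial mediation, and no direct or indirect effect is to be estimated

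*Combined protocol and SAP*

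**What the plan says.** The overview that closes the Significance section predicts that CBD will increase talkativeness and that weaker responses to negative stimuli will mediate this.

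The IST paragraph of Data Analysis sets the test. "Following criteria for within-subject mediation", it first asks whether Drug affects word count. Then: "We will then include the per-participant estimates of the effect of drug on responses to negative stimuli as covariates". Two checks follow:

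- Check 1: "Whether changes in responses to negative stimuli account for a significant proportion of changes in talkativeness".
- Check 2: "Whether the effect of drug on talkativeness is still significant after inclusion of the changes in responses to negative stimuli".

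The closing sentence begins "If the effect of drug on effort is wholly mediated by changes in responses to negative stimuli" and says that the drug effect on talkativeness should then no longer be "significant after including drug-induced changes in responses to negative stimuli as a covariate". *Effort* there is evidently a slip for talkativeness.

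The Exploratory Analysis of Relationship to Mood follows the same procedure, with anxiety, sedation and euphoria as covariates, to establish whether effects on negative-stimulus responses are partly or wholly mediated by mood.

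Neither paragraph plans an estimate or interval for the indirect effect (through the mediator) or the direct effect (what remains). The candidate mediators are the seven dependent variables modelled for the three tasks (IAPS three, DEIT two, ABT two). The text does not say which enter, whether jointly, or what form the covariate takes. Euphoria is drawn from three instruments, and mood is measured six times per session; none is selected.

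**The concern.** Check 1 bears on whether there is any mediation. Only check 2 separates whole from partial, and it does so by reading a p-value above the threshold as absence of a direct effect.

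It can fail both ways. A real direct effect about half the size of the total may miss significance in 36 people and look wholly mediated. Conversely, error in the mediator shrinks its slope, so part of a fully mediated effect is credited to Drug and mediation looks partial.

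At stake is the mechanistic account of any talkativeness effect, and of the mood analysis. A significance pattern would be reported where the reader needs to know how much of the effect passes through the mediator, and how precisely that is known.

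**Working it through.** **From the documents.** 36 expected completers (Subjects) and four sessions (Design), so 36 × 4 = 144 word counts. There is no mediation figure in the plan to reproduce. Alpha is not stated; 0.05 two-sided is assumed.

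**Step 1: one active-minus-placebo contrast.** Suppose the total effect is just large enough for 90% power: standardised paired effect = (1.96 + 1.28)/√36 = 0.54. If a share p is mediated, the direct effect has expected z = 0.54 × (1 − p) × 6. Ignoring the precision lost by adding the mediator:

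| Share mediated | Expected z | Chance Drug is non-significant |
|---|---|---|
| 25% | 2.43 | 32% |
| 50% | 1.62 | 63% |
| 75% | 0.81 | 87% |
| 100% | 0 | 95% |

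Non-significance is the likelier result at 50%, 75% and 100% alike.

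**Step 2: the four-session model, both checks applied.** Assumed values:

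- Mediator means 0, 0.2, 0.4, 0.6 for placebo, 300, 600 and 900 mg.
- Mediator SDs 0.7 between participants, 0.3 per active dose, 0.4 session noise.
- Outcome SDs 0.7 between participants, 0.5 residual.
- Total effects on word count 0, 0.2, 0.4, 0.6 (standardised units).

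The mediator is a session value centred within participant, beside Drug, with a random intercept. Drug is tested on 3 df, with 144 − 36 − 3 − 1 = 104 residual df. Only trials with a significant total effect are counted. The whole-mediation pattern means check 1 is met and Drug is no longer significant.

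| Truth (no mediator error) | Whole-mediation pattern |
|---|---|
| No mediation, independent errors | 0.3% |
| Quarter mediated | 14% |
| Half mediated | 53% |
| Three quarters mediated | 85% |
| Complete | 96% |

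For half mediation, scaling all assumed effects by 0.5, 1.5 and 2 gives about 68%, 27% and 14%. Entering the mediator as uncentred change from placebo gives 48% at the base effects, and 65%, 22% and 8% at those scalings.

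**Step 3: mediator error under complete mediation.** The true mediator's within-participant variance around the dose means is (0.16 + 3 × 0.25)/4 = 0.2275. Error variance is 0.2275 × (1/0.7 − 1) = 0.0975 at reliability 0.7, and 0.2275 at 0.5. Error multiplies the slope by the reliability, so the expected Drug coefficient at 900 mg, truly zero, becomes:

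- reliability 0.7: 0.6 × (1 − 0.7) = 0.18;
- reliability 0.5: 0.6 × (1 − 0.5) = 0.30.

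The second equals the true direct effect of a half-mediated drug measured without error (0.6 × 0.5 = 0.30), so the significance of Drug cannot tell these two cases apart. In simulation Drug stayed significant in about 5%, 19% and 40% at reliability 1, 0.7 and 0.5.

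**Step 4: shared session-level causes.** With no mediation but a residual correlation of 0.2 or 0.4 between mediator and word count (alertness, for example), the whole-mediation pattern appears in 8.5% and 31%.

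**The case against.** The strongest reply is about weight. The IST sentence runs one way: whole mediation implies loss of significance. It does not say that loss of significance proves whole mediation. Aim 3 needs only mediation, and for that check 1 does reasonable work: in a simulation with one error-free mediator and no shared cause, it was met in 5.6% of trials with no mediation and over 99% with half. Only the mood analysis, labelled exploratory, undertakes to settle partial versus whole. All this stands and limits the point. It does not rescue check 2, which the IST paragraph sets out to examine and the mood analysis relies on.

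The magnitudes also rest on assumed effects. That stands too: the half-mediated figure varies widely, though the direction held in every setting run.

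Two stronger readings are tempting. A reader might infer that one value per participant is entered as a main effect. With complete data the Drug contrasts could then not move, and check 2 could never show mediation. But the references to drug-induced changes and to within-subject criteria suggest a change per dose, and the cited criteria and worked example, which are not in the documents, may define it. A reader might also infer that the seven measures are tried one at a time, giving 1 − 0.95^7 = 30% chance of at least one false association if independent. The plan does not say so, and its plural *covariates* allows joint entry. Neither reading is established.

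**Conclusion.** The point holds and should be fixed, within limits. As planned, the analysis cannot separate whole from partial mediation, and it provides no estimate that would show how much is mediated. Under the assumed effects, a half-mediated effect looks wholly mediated in about 53% of trials (14% to 68% over the effect sizes tried, session-level form), and a completely mediated one leaves Drug significant in about 5% to 40% depending on mediator reliability. These figures illustrate; they do not predict this trial.

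A reader might go further and conclude that Aim 3 fails or that mediation will routinely be declared where none exists. The documents do not support that. The first-step test of Drug on word count is untouched, mediation is examined only after that effect is established, and with no mediation and independent errors the whole-mediation pattern occurs in under 1%. The incomplete description of the mediator is a secondary gap, and *effort* is clerical.

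**What to change.** In the IST and mood paragraphs:

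1. Replace the significance criterion with the estimated indirect and direct effects of each dose, with participant-level bootstrap 95% confidence intervals. Drop the whole and partial labels.
2. Do not substitute a threshold label. With half the total effect (0.30) as the bound at 900 mg, a rule that the interval excludes 0.30 is also met by intervals lying wholly above it (about 65% of no-mediation trials). A one-sided version is met in about 62% to 66% of completely mediated trials without error, but in only 15% and 3% at reliability 0.7 and 0.5, and still in 22% when three quarters is mediated. A two-sided version is met in 28% under complete mediation.
3. Define the mediator as the mean negative-stimulus response in each session, one pre-named measure per task, centred within participant, beside Drug with a random intercept for Subject. Enter the three tasks jointly as the main analysis. With all four sessions present, centring makes session values and change from placebo the same covariate.
4. For mood, pre-name one euphoria scale and use the last assessment completed before the first task. First reconcile the start times: the Study Session text puts tasks about 90 minutes after the 1:30 pm capsule (about 3:00 pm), while the Timeline gives 4:00 pm. The 3:45 pm assessment falls during the tasks on one and before them on the other.
5. State two limits. The indirect effect is not causal if session-level causes are shared: with no mediation its interval excluded zero in about 56% and 99% of trials at residual correlation 0.2 and 0.4. Mediator error biases it toward zero. Report results over a range of assumed correlations and, where trials can be split in half, a reliability-corrected estimate.
6. Correct *effort* to talkativeness.

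The cost is revised analysis wording and a modest amount of extra analysis, with no new data. The price is wide intervals, a weaker causal claim and low power for single tasks: with half the effect mediated and spread over three tasks, each per-task interval excluded zero in 21% to 41%. Thirty-six completers could not establish whole mediation under either approach.

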Detailed Protocol

Title: Effects of cannabidiol on responses to emotional stimuli (“Effects of drugs on mood and behavior” on the consent form)

P.I.: [name]

Co-Investigators: [name], [name], [name]

May 11, 2016

Objectives: To study the effects of cannabidiol (CBD), a constituent of marijuana, on responses to emotional stimuli in healthy young adults.

Aim 1. We will assess the effects of CBD on subjective and psychophysiological responses to images with positive (rewarding) vs. negative (aversive) emotional content. Our working hypothesis is that CBD will reduce subjective and psychophysiological responses to negative images without affecting responses to positive images.

Aim 2. We will examine the effect of CBD on responses to the socially rewarding and aversive information conveyed by emotional facial expressions. We will measure speed of identification for positive (rewarding) and negative (aversive) emotional expressions as they dynamically develop, psychophysiological reactions to emotional expressions and direction of attention to emotional expressions. Our working hypothesis is that CBD will slow identification of negative expressions, reduce psychophysiological responses to negative expressions, and reduce direction of attention to negative expressions without affecting responses to positive expressions.

Aim 3. We will examine the effect of cannabidiol on a controlled social interaction with a research assistant. Our working hypothesis is that the reduction in responses to negative emotional and social stimuli produced by CBD will result in greater talkativeness in a controlled social interaction.

Exploratory Aim. We will additionally measure the effects of CBD on subjective mood, including anxiety, euphoria and sedation, to determine whether the CBD’s effects on responses to emotional stimuli are mediated by effects on subjective mood, or occur above and beyond CBD-induced changes in mood.

Significance

The purpose of this project is to investigate the effects of cannabidiol (CBD) on responses to emotional stimuli in humans. CBD is one of the primary constituents in whole plant marijuana (Ashton 2001). Such cannabinoid compounds are of interest for two reasons. First, understanding the effects of these compounds may shed light on the phenomena of marijuana use and abuse. Second, studying the effects of cannabinoids may be informative about the purposes and functioning of the brain’s endocannabinoid

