system. This system has recently been the focus of much therapeutic interest due to its involvement in stress and eating disorders (Felder 2006). Most research on cannabinoids has focused on delta-9-tetrahydrocannabinol, the primary psychoactive ingredient in marijuana and the chemical that appears to be most responsible for the typical subjective effects of marijuana (Ilan et al. 2005). However, cannabidiol has recently become a focus of interest for two reasons. First, it appears to dampen some of the anxiogenic effects of THC, which may contribute to the reinforcing effects of whole plant marijuana (Zuardi et al. 1982). Second, cannabidiol may have anxiolytic effects in and of itself (Bergamaschi et al. 2011b; Crippa et al. 2011; Fusar-Poli P and et al. 2009; Zuardi et al. 1993). At this point, the neural mechanisms by which cannabidiol produces these effects are unknown. Cannabidiol does not appear to have direct actions at either of the endocannabinoid receptors, although it can antagonize the effects of cannabinoid agonists. It may act as an antagonist at the putative new cannabinoid receptor, GPR55, and it may act as a 5-HT_{1A} receptor agonist as well as a modulator at opioid receptor sites (Pertwee 2008).

Our primary interest here is in the potential anxiolytic properties of CBD. In animals, CBD increases exploratory behavior in the elevated plus maze, and reduces freezing in a conditioned environment and in response to exposure to a predator, suggesting anxiolysis (Schier et al. 2012). These effects were comparable to those of diazepam, a benzodiazepine and known anxiolytic, but were mediated by different neurochemical mechanisms (Schier et al. 2012). In humans, CBD reduced anxiety in responses to public speaking in both healthy volunteers and individual with social anxiety disorder (Bergamaschi et al. 2011b; Zuardi et al. 1993), reduced amygdala responses to fearful faces (Bhattacharyya et al. 2009; Fusar-Poli P and et al. 2009), and reduced subjective anxiety in response to a stressful imaging procedure (Crippa et al. 2003). Importantly, CBD also produced less sedation when compared to the traditional anxiolytic diazepam (Zuardi et al. 1993). Together, these findings suggest CBD has anxiolytic properties that may be comparable to those of traditional drugs, but that are mediated through different neural mechanisms and potentially produce fewer sedative side-effects.

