Program will be used to examine the total number of words as an index of social activity, and the amount of positivity and the amount of negativity expressed in each speech task, as a behavioral index of affect (Pennebaker et al. 2007).

Subjective Measures:

1. Profile of Mood States – POMS (McNair et al. 1971). The POMS is a validated measure consisting of 72 adjectives commonly used to describe momentary mood states. The POMS is highly sensitive to the effects of drugs in similar samples of healthy volunteers (de Wit & Griffiths, 1991; Johanson & Uhlenhuth, 1980), and will be used to assess mood effects of the drug during the study sessions.
2. Drug Effects Questionnaire – DEQ (Fischman and Foltin 1991). The DEQ is a validated measure consisting of questions on a visual analog scale about the subjective effects of drugs. Subjects are asked to rate the extent they feel a drug effect, whether they like or dislike the drug effect, and if given a choice would they want to take more of the drug. This is also be used to assess the pharmacodynamics of the drug effect during the study
3. The Addiction Centre Research Inventory – ARCI (Martin et al. 1971). The ARCI is a true-false questionnaire that consists of empirically derived scales sensitive to the effects of a variety of classes of psychoactive drugs (Haertzen 1966). We used a 53-item version, which yields scores for six scales that include: sedation (Pentobarbital-Chlorpromazine Group; PCAG), stimulant-like effects (Amphetamine; A, and Benzedrine Group; BG), somatic and dysphoric effects (Lysergic Acid; LSD), euphoria (Morphine-Benzedrine Group; MBG), and marijuana-like effects (M).
4. The Evaluative Space Grid – ESG (Larsen et al. 2009). The Evaluative Space Grid is validated measure consisting of a two dimensional grid that provides a single item measure of positivity and negativity. This will be used to measure subjective reactions to the IAPS pictures.

Psychophysiological Measures:

1. Cardiovascular measures – Blood pressure and heart rate will be periodically monitored using portable blood pressure cuffs, to track the cardiovascular effects of the drug, and ensure participant safety.

Procedure:

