Exploratory Analysis of Relationship to Mood: We will conduct similar within-subject mediational Mixed Linear Model analyses in R using lme4 on our primary outcomes of responses to negative stimuli, using subjective measures of anxiety (from the POMS), sedation (from the ARCI) and euphoria (from the POMS, ARCI and DEQ) as covariates. Following the procedure described above, we will determine whether the effects of the drug on responses to negative stimuli are partially or wholly mediated by its effects on subjective mood.

Human Subjects Information

Recruiting methods: We will place print ads in newspapers and on online job search sites such as craigslist.org, and flyer in the Chicago area. Healthy volunteers who respond to our ads are screened using our standard screening protocol for all studies in the Human Behavioral Psychopharmacology Laboratory, which is separately approved by the IRB under Protocol #13681B.

Obtaining consent: Written informed consent for the screening session only is obtained at the screening according to procedures outlined in Protocol #13681B. Written informed consent for the study procedures is obtained at the orientation session, after a verbal explanation of study procedures, check of comprehension, and an opportunity for the participant to ask any questions they may have. Consent is verbally re-verified at the beginning of each study session.

Risk to subjects:

1. Diagnostic procedures and questionnaires: Some of the questions asked during the screening may be considered sensitive information, including drug use history and psychiatric history. We have rigorous procedures in place to ensure confidentiality of data, including locked cabinets for confidential files, subject coding, secure computer systems, and rigorous training of personnel. Please see screening protocol #13681B for full information on steps taken to protect information gathered as part of the screening.

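### The written mood-mediation steps never test whether CBD changed mood, so a mood score that merely correlates with the response can be reported as a partial mediator

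*Combined protocol and SAP*

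**What the plan says.** The Exploratory Aim under Objectives states: "We will additionally measure the effects of CBD on subjective mood, including anxiety, euphoria and sedation". The Timeline schedules POMS, DEQ, ARCI and cardiovascular measures six times per session (1:15, 2:15, 3:00, 3:45, 5:00 and 5:45pm).

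The Data Analysis section specifies these outcomes:

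- IAPS: "on each dependent variable (subjective ratings, corrugator and startle responses"
- DEIT: "on each dependent variable (expression intensity and corrugator responses"
- ABT: a generalized mixed model "on the binomial variable of initial gaze direction with Drug (0, 300, 600 and 900mg", and a linear mixed model for total dwell time
- IST: total word count

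In the last subsection, on the relationship to mood, POMS anxiety, ARCI sedation and euphoria (POMS, ARCI and DEQ) enter as covariates in models of the responses to negative stimuli. That subsection adopts the IST mediation procedure by reference and will conclude whether the drug effects "are partially or wholly mediated by its effects on subjective mood".

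The IST procedure has three tests:

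1. Does drug affect the outcome?
2. "Whether changes in responses to negative stimuli account for a significant proportion of changes in talkativeness"
3. Is the drug effect still significant once the covariate is included?

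**The concern.** Mediation by mood has two links: drug changes mood, and mood changes the response. The three written tests cover the second link and the total and adjusted drug effects. None covers the first.

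For Aim 3 this does little harm, because the proposed mediators are the IAPS, DEIT and ABT responses and each has its own model with Drug as a factor. For mood no written model does that job.

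A participant who is more anxious or tired on one day may rate pictures differently that day whether or not CBD had anything to do with it. Under the written steps, that ordinary correlation is enough for the mood score to pass the second test. The report could then attribute part of CBD's effect to a mood change that did not occur.

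**Working it through.** **Reading the text.** The modelled outcomes are picture ratings, corrugator, startle, expression intensity, gaze direction, dwell time and word count. None is a mood measure. The plan states no alpha, effect size or error rate for mediation, so there is no figure of its own to reproduce.

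**Inputs.** From the documents: 36 expected completers (Subjects) and four within-subject dose levels, 0, 300, 600 and 900 mg (Design). Assumed: alpha 0.05; a CBD effect δ on the response, linear in dose, of 0.6 or 0.8 within-subject SD at 900 mg; a within-subject mood–response correlation ρ of 0.2, 0.3 or 0.5; one session-level mood covariate.

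**Model.** For participant i and session j, mood is M = u, with no dose term. The response is Y = δ × dose/900 + ρu + √(1 − ρ²)z, with u and z independent standard normal. Subject means are removed, as an approximation to the lme4 model. The tests are:

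- Drug on Y: F on 3 and (36 − 1) × 3 = 105 df
- Mood covariate given Drug: F on 1 and 104 df
- Drug given mood: F on 3 and 104 df

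I count *partial* when all three are significant, and *whole* when the first two are significant and the third is not. The plan defines only whole mediation. The rule for partial is my inference from the steps.

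**Why the covariate passes.** With true drug-to-mood effect a = 0, the indirect effect is a × b = 0 × ρ = 0, so there is nothing to mediate. The covariate test still has noncentrality of about 105 × ρ²/(1 − ρ²):

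- ρ = 0.2: 105 × 0.0417 = 4.4, root 2.09, power about Φ(2.09 − 1.98) = 54%
- ρ = 0.3: 105 × 0.0989 = 10.4, root 3.22, power about Φ(3.22 − 1.98) = 89%
- ρ = 0.5: 105 × 0.333 = 35, root 5.92, power about 100%

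The first test has power of about 58% at δ = 0.6 and 85% at δ = 0.8. The products are 31%, 52% and 58% at δ = 0.6, and 46%, 76% and 85% at δ = 0.8.

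**Simulation** (20,000 trials per row, true CBD effect on mood zero):

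| δ | ρ | Partial | Whole | Either | Either, and drug-on-mood significant |
|---|---|---|---|---|---|
| 0.6 | 0.2 | 29.9% | 1.6% | 31.5% | 1.4% |
| 0.6 | 0.3 | 47.9% | 2.9% | 50.9% | 2.4% |
| 0.6 | 0.5 | 55.1% | 3.1% | 58.2% | 3.1% |
| 0.8 | 0.2 | 45.3% | 0.8% | 46.1% | 2.1% |
| 0.8 | 0.3 | 73.3% | 1.5% | 74.8% | 3.8% |
| 0.8 | 0.5 | 84.5% | 0.9% | 85.4% | 4.2% |

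Repeat runs move these by a point or two, so I quote about 29–84% for partial and 1–4% for whole. With ρ = 0, a mediation verdict occurs in only about 5% of the trials that show a drug effect on the response.

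**Would a significance gate do instead?** The last column shows that a required drug-on-mood F test removes most false verdicts. It also rejects real effects: true mood effects of 0.3, 0.4, 0.5 and 0.6 SD at 900 mg pass the gate in about 17%, 28%, 42% and 58% of trials.

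**The case against.** **The defined verdict is rarely wrong.** The only verdict with a stated rule is whole mediation, and it is falsely reached in about 1–4% of trials. This stands. But the mood subsection also offers partial mediation as a conclusion and gives no rule to keep it from being used here.

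**A reader might infer that the rule answers the Exploratory Aim backwards.** The documents do not support that. The aim asks whether CBD's effects go beyond mood changes, and the third test addresses this directly. When CBD leaves mood alone, drug usually stays significant, which is the right answer. The error is a false partial label beside it.

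**The covariate may differ from the one simulated.** The IST procedure enters per-participant estimates of the drug effect, whereas the mood subsection speaks of subjective measures as covariates. On the first reading some unwritten mood model would have to exist, and the percentages above would not carry over directly. The gap would remain, because estimates that scatter around zero can still predict the response, and deriving them is not testing them.

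**The cited within-subject mediation criteria may include the missing step.** That cannot be checked from the documents. The finding is limited to what the plan writes out.

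**A reader might also infer that the main question is never estimated,** given the statement "Our primary interest here is in the potential anxiolytic properties of CBD". This goes too far. The plan expresses anxiolysis as reduced responses to aversive stimuli, which are modelled. Subjective mood is explicitly exploratory. Blood pressure and heart rate are collected "to track the cardiovascular effects of the drug" and for safety, but they are not proposed mediators, so the lack of a model for them is a separate matter.

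**Conclusion.** The point holds in a limited form. No written model has anxiety, sedation or euphoria as its outcome, and the adopted steps omit the drug-to-mood link. A partial-mediation statement can therefore be made when CBD did not change mood.

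If session mood scores are the covariates, the risk is about 29–84% of trials over the assumed range. It depends mainly on the mood–response correlation and on the power for the drug effect, neither of which the plan gives. False whole mediation is a minor risk. The analysis is exploratory, so the damage is confined to how a drug effect is explained and does not reach whether one is found. It still deserves correction, because following the written steps faithfully can produce the misleading statement.

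**What to change.** In the mood subsection of Data Analysis:

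1. For each named measure (POMS anxiety, ARCI PCAG sedation, and one euphoria scale chosen in advance), fit a mixed model with Drug and time, and with the same-session 1:15pm value as a covariate. Report CBD-minus-placebo differences with 95% CIs.
2. Base any statement of partial or whole mediation on the indirect effect (drug-to-mood times mood-to-response) with a 95% CI. Do not base it on significance of the mood covariate, or on a drug-on-mood significance gate alone.
3. Where that interval includes zero, report mood as a covariate and say that mediation was not shown, rather than that it was ruled out.

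The cost is some wording and a few extra models on data already scheduled for collection, with no added visits or participants. The downside is fewer mediation claims.
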